12.7 Reference Population

As discussed in the introduction (Section 1.1), in a prior study of neoadjuvant Sipuleucel-T, a negative control was felt to be important to be confident that the observed changes in the study population were due to treatment effect since the effect of systemic Sip-T administration on localized prostate cancer was unknown. Therefore, a group of 12 patients who had undergone RP at UCSF without any neoadjuvant therapy, were selected prior to undergoing any tissue analyses, and were matched to the study population using the UCSF CAPRA-S score for preoperative risk stratification - were used as a negative control. These patients were selected from the surgical population at UCSF who provided separate, written consent to the use of their RP specimens for research purposes.

Similarly, in this study, a cohort of 12 patients not treated with any neoadjuvant therapy will be used as a negative control, since the effect of neoadjuvant ibrutinib in prostate cancer tissue is unknown. Patients will be selected from the RP population at UCSF or Washington University who provided separate, written consent to the use of their RP specimens for research purposes, and will be matched to the phase II study population using the UCSF CAPRA-S score for preoperative risk stratification. This analysis will provide confidence that the changes observed in the prostates of treated patients are due to neoadjuvant treatment effect. These 12 patients will not otherwise be included in the analyses as delineated in 12.6.

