12.6.4 Analysis of Exploratory Endpoints

12.6.4.1 Assessment of Btk expression

Btk expression on tumor tissue from pre-treatment biopsies, RP specimens, and any other tumor biospecimens obtained will be evaluated immunohistochemically and graded as low, intermediate or high. Frequency distribution and percentage will be used to summarize Btk expression by pre- and post- treatment. In addition, Kappa statistics will be used to test if there is any change of Btk expression from pre-treatment biopsy to post-treatment RP tissue.

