12.6.4.2 Assessment of PD-L1 expression

PD-L1 protein expression on tumor tissue from pre-treatment biopsies, RP specimens, and any other tumor biospecimens obtained will be evaluated immunohistochemically and scored on a scale of 0, 1, 2, or 3. We will categorize tumors based on the frequency of tumor cells or of immune cells staining positively for PD-L1 as follows: IHC 0: $<1\%$, IHC 1: $1-5\%$, IHC 2: $5-10\%$ and IHC 3: $\geq 10\%$. Frequency distribution and percentage will be used to summarize PD-L1 protein expression by pre- and post- treatment. Furthermore, McNemar's test will be used to assess the impact of the treatment on PD-L1 expression by considering IHC estimates of $\geq 10\%$ as being positive.

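### Section 12.6.4.2 reads a biopsy-versus-prostatectomy McNemar test as the impact of ibrutinib on PD-L1, but drug and specimen type change together and the untreated reference prostatectomies are not planned for this marker

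*Combined protocol and SAP*

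**What the plan says.** Section 12.6.4.2 scores PD-L1 from 0 to 3 on "pre-treatment biopsies, RP specimens, and any other tumor biospecimens obtained", treats staining of 10% or more as positive, and says that "McNemar's test will be used to assess the impact of the treatment on PD-L1 expression". The objective in section 2.1.3 is likewise causal: to determine what neoadjuvant ibrutinib does to PD-L1. Section 1.5 presents the biopsy-to-prostatectomy comparison, with PD-L1 and Btk on its list, as the way to evaluate the effects of ibrutinib.

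Section 12.7 recalls a prior neoadjuvant study in which "a negative control was felt to be important to be confident that the observed changes in the study population were due to treatment effect". It adopts the same device here: "a cohort of 12 patients not treated with any neoadjuvant therapy will be used as a negative control". The controls are patients who gave "separate, written consent to the use of their RP specimens for research purposes, and will be matched" on CAPRA-S, and the stated purpose is that "This analysis will provide confidence that the changes observed in the prostates of treated patients are due to neoadjuvant treatment effect". The section closes: "These 12 patients will not otherwise be included in the analyses as delineated in 12.6".

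Reference tissue appears in two other places that matter here: the B- and T-cell infiltration endpoint (2.2.1) and the descriptive summary of infiltration (12.6.2.2). Neither covers PD-L1.

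For Btk, section 12.6.4.1 is more guarded. It asks only about "any change of Btk expression from pre-treatment biopsy to post-treatment RP tissue".

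**The concern.** In each pair the first specimen is a needle core, possibly archival (3.3.1, 8.1.1.2), taken before the drug. The second is a prostatectomy taken after it. Pairing removes differences between patients, but not a difference between specimen types that runs in the same direction in every patient. If RP tissue tends to read higher or lower for PD-L1 than core tissue, for example through the area sampled or through handling, McNemar's test will pick that up and 12.6.4.2 will label it a treatment effect.

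Section 12.7 gives the reason for having a control: the effect of ibrutinib in prostate tissue is unknown. That reason applies to PD-L1 as much as to infiltrating lymphocytes. Section 1.3 says the study's findings may justify further work, including combination therapy, and it cites preclinical enhancement of anti-PD-L1 activity. A PD-L1 shift wrongly credited to the drug could feed into that argument.

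**Working it through.** The plan states no error rate, power, significance level or sidedness for the PD-L1 test, so there is no figure to reproduce. The power statement in 12.3 concerns the B-cell endpoint and does not bear on this point.

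**Inputs.** n = 24 pairs (12.3), assuming every patient has two evaluable specimens. 12 reference RPs (12.7). Two-sided 0.05, assumed. Discordance rates, assumed.

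**1. False attribution with no drug effect.** Let b be the number of patients positive on RP only and c the number positive on biopsy only. The exact test has p = 2 × P(Bin(b + c, ½) ≤ min(b, c)), capped at 1.

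- 5 v 0 gives 2 × (½)^5 = 0.0625, not significant.
- 6 v 0 gives 2 × (½)^6 = 0.031, significant.
- 8 v 1 gives 2 × (1 + 9)/512 = 0.039, significant.

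The chance of rejection is the sum, over all (b, c) with p ≤ 0.05, of 24!/[b! c! (24−b−c)!] × π_b^b × π_c^c × (1−π_b−π_c)^(24−b−c). Here π_b and π_c come from specimen type alone.

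| RP only / biopsy only | Expected b v c (24 × rate) | Rejection, no drug effect |
|---|---|---|
| 5% / 5% | 1.2 v 1.2 | 0.1% |
| 10% / 5% | 2.4 v 1.2 | 1.1% |
| 15% / 5% | 3.6 v 1.2 | 5.6% |
| 20% / 5% | 4.8 v 1.2 | 15% |
| 25% / 5% | 6.0 v 1.2 | 28% |
| 30% / 5% | 7.2 v 1.2 | 43% |

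If the two specimen types stain alike, the test is conservative. The error appears only when discordance is lopsided, and it then grows quickly.

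**2. What the reference RPs can do.** Treated RP versus reference RP is a comparison within one specimen type. With no drug effect, Fisher's exact test on 24 v 12 rejects in 1.6% to 2.9% of trials for common positivity of 10% to 40%, whatever the biopsy-to-RP shift.

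Precision is limited. In SD units, the difference detectable with 80% power is about (1.96 + 0.84) × √(1/24 + 1/12) = 2.80 × 0.354 = 0.99, or 1.02 with the t distribution on 34 df. On the binary scale, power is 0.15 for 10% v 30%, 0.39 for 10% v 40%, 0.65 for 10% v 50% and 0.85 for 10% v 60%.

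**3. How strict the check must be.** The same treated RPs enter both comparisons, so mere agreement in direction is a weak safeguard. This was simulated with no drug effect, gamma-distributed staining with mean 3% or 6%, and RP tissue reading 1.5 to 2 times higher than core, all assumed. About 60% to 78% of false McNemar increases were accompanied by treated RPs ranking above reference RPs. Only about 4% to 11% were accompanied by a significant rank-sum result.

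**The case against.** The strongest reply is that this is an exploratory endpoint with no decision rule attached, and that the control tissue is assigned where it matters most, to the primary infiltration objective. The error rates rest on assumed discordance, and with like staining the risk is negligible. There are no reference biopsies, so the control cannot estimate the biopsy-to-RP shift itself. Reference RPs may come from UCSF or Washington University (12.7), while section 6.1.3 places study RPs at Washington University, so shared staining batches would not remove site or fixation differences. All of this stands. It limits the size of the point and what the fix can deliver, but it does not make the causal label in 12.6.4.2 sound.

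A reader might infer more than the documents support:

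- **That Btk is also reported as an effect of ibrutinib.** Section 12.6.4.1 claims only a change, and the Btk objective in 2.1.3 is descriptive. The attribution comes from the general framing in 1.5.
- **That 12.7 forbids staining the reference tissue for PD-L1.** It does not. Section 12.6.2.2 is itself part of 12.6 and uses reference tissue, so the closing sentence is not a total exclusion. What is missing is any plan to use it for this marker. The phrase about other biospecimens in 12.6.4.2 names no such comparison.
- **That control tissue is already in hand.** Section 12.7 says the patients will be selected.
- **That a high false-positive rate has been shown.** It has not. The table gives a range over assumptions.

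**Conclusion.** The point holds for PD-L1. The McNemar test in 12.6.4.2 estimates a biopsy-to-RP difference in which drug and specimen type cannot be separated, and the plan calls it the impact of treatment without using the control that 12.7 says gives confidence in such a claim. With no drug effect, the chance of a significant result runs from 0.1% under symmetric 5%/5% discordance to 43% at 30%/5%. This assumes 24 evaluable pairs and an exact two-sided test at 0.05. The true discordance is unknown, so the range shows sensitivity and does not predict the error rate.

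For Btk the weakness is milder, since the analysis text claims only a change. Both endpoints are exploratory, and neither the primary endpoint nor its conclusion is affected.

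**What to change.** 1. In 12.6.4.2, describe the McNemar result as a biopsy-to-RP difference and drop the reference to the impact of treatment.
2. Amend the last sentence of 12.7 so that the reference RPs are also stained for PD-L1, coded and mixed into the same batches as the treated RPs. Report the treated-RP versus reference-RP ordinal scores with an estimate of the difference, a 95% confidence interval and a Wilcoxon rank-sum test.
3. Base any attribution to ibrutinib on that RP-to-RP comparison, requiring a confidence interval that excludes no difference. Agreement in direction with the McNemar result is not enough. State that with 24 v 12 only differences of about 1 SD are detectable with 80% power, so a null result does not rule out an effect.
4. Optionally, add the same descriptive comparison for Btk. Section 9.1.5 names total Btk and phospho-Btk, so this means two further stains.

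The cost is one stain (three with Btk) on 12 specimens already planned for immunohistochemistry, subject to available sections and the scope of consent, and a more cautious claim. No new patients or procedures are needed. The source site of each reference RP should be reported, because site or fixation differences may remain.

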12.8 Evaluation of Safety

Analyses will be performed for all patients having received at least one dose of study drug. The study will use the NCI CTCAE v4.0.

12.9 UCSF's Data

Data from the first three patients enrolled at UCSF will be shared with Washington University under a Data Use Agreement and analyzed under the auspices of this study.

APPENDIX 1: PERFORMANCE STATUS CRITERIA

ECOG Performance Status Scale	
Grade	Descriptions
0	Normal activity Fully active, able to carry on all pre-disease performance without restriction
1	Symptoms, but ambulatory Restricted in physically strenuous activity, but ambulatory and able to carry out work of a light or sedentary nature (e.g., light housework, office work)
2	In bed < 50% of the time Ambulatory and capable of all self-care, but unable to carry out any work activities Up and about more than 50% of waking hours
3	In bed > 50% of the time Capable of only limited self-care, confined to bed or chair more than 50% of waking hours
4	100% bedridden Completely disabled Cannot carry on any self-care Totally confined to bed or chair
5	Dead

APPENDIX 2: Prohibited and Restricted Medications

Generic name	Trade/Brand name (if applicable)
Bicalutamide	Casodex
Carbamazepine	Tegretol
Celecoxib	Celebrex
Ciprofloxacin	Cipro
Clarithromycin	Biaxin
Clopidogrel	Plavix
Dexamethasone	Decadron
Diltiazem	Cardizem
Enoxaparin	Lovenox
Finasteride	Proscar
Fluconazole	Diflucan
Flutamide	Eulexin
Itraconazole	Onmel, Sporanox
Ketoconazole	
Nilutamide	Nilandron
Phenytoin	Dilantin
Prednisone	Sterapred
Rifampin	Rifadin
Telithromycin	Ketek
Verapamil	Calan
Warfarin	Coumadin

Notes:

1. This list is not meant to be all-inclusive.
2. Any medications known to cause QT prolongation should be used with caution. Periodic ECG and electrolyte monitoring should be considered.

APPENDIX 3: SPECIMEN COLLECTION

A: For tissue analyses:

Paired pre- and post- treatment tumor tissue specimens will be collected in all patients and analysis will be performed per section 8. Specimens will be processed initially through the Tissue Procurement Core Facility.

B: For blood analyses:

All patients will have 8 (eight) 10mL tubes of blood specimens collected at baseline, at the end of ibrutinib therapy, and after RP. The collection will be divided into 60 mL in 6 EDTA tubes for PBMCs for immune monitoring and 20 mL in 2 EDTA tubes for plasma for cytokines.:.

These specimens will be transported at room temperature to the Tissue Procurement Core Facility where they will be processed using their SOPs to obtain plasma and PBMCs.

APPENDIX 4: CHILD-PUGH SCORE

Measure	1 point	2 points	3 points
Total bilirubin, μ mol/L (mg/dL)	<34 (<2)	34-50 (2-3)	>50 (>3)
Serum albumin, g/L (g/dL)	>35 (>3.5)	28-35 (2.8-3.5)	<28 (<2.8)
PT INR	<1.7	1.71-2.30	>2.30
Ascites	None	Mild	Moderate to Severe
Hepatic encephalopathy	None	Grade I-II (or suppressed with medication)	Grade III-IV (or refractory)

Points	Class
5-6	A
7-9	B
10-15	C

Source:

APPENDIX 5: Definitions for Adverse Event Reporting

A. Adverse Events (AEs)

As defined in 21 CFR 312.32:

Definition: any untoward medical occurrence associated with the use of a drug in humans, whether or not considered drug-related.

Grading: the descriptions and grading scales found in the revised NCI Common Terminology Criteria for Adverse Events (CTCAE) version 4.0 will be utilized for all toxicity reporting. A copy of the CTCAE version 4.0 can be downloaded from the CTEP website.

Attribution (relatedness), Expectedness, and Seriousness: the definitions for the terms listed that should be used are those provided by the Department of Health and Human Services' Office for Human Research Protections (OHRP). A copy of this guidance can be found on OHRP's website:

<http://www.hhs.gov/ohrp/policy/advevntguid.html>

B. Suspected Adverse Reaction (SAR)

As defined in 21 CFR 312.32:

Definition: any adverse event for which there is a reasonable possibility that the drug caused the adverse event. “Reasonable possibility” means there is evidence to suggest a causal relationship between the drug and the adverse event. “Suspected adverse reaction” implies a lesser degree of certainty about causality than adverse reaction, which means any adverse event caused by a drug.

C. Life-Threatening Adverse Event / Life Threatening Suspected Adverse Reaction

As defined in 21 CFR 312.32:

Definition: any adverse drug event or suspected adverse reaction is considered “life-threatening” if, in the view of the investigator, its occurrence places the patient at immediate risk of death. It does not include an adverse event or suspected adverse reaction that, had it occurred in a more severe form, might have caused death.

D. Serious Adverse Event (SAE) or Serious Suspected Adverse Reaction

As defined in 21 CFR 312.32:

Definition: an adverse event or suspected adverse reaction is considered “serious” if, in the view of the investigator, it results in any of the following outcomes:

- Death
- A life-threatening adverse event
- Inpatient hospitalization or prolongation of existing hospitalization

- A persistent or significant incapacity or substantial disruption of the ability to conduct normal life functions
- A congenital anomaly/birth defect
- Any other important medical event that does not fit the criteria above but, based upon appropriate medical judgment, may jeopardize the subject and may require medical or surgical intervention to prevent one of the outcomes listed above

E. Protocol Exceptions

Definition: A planned change in the conduct of the research for one participant.

F. Deviation

Definition: Any alteration or modification to the IRB-approved research without prospective IRB approval. The term “research” encompasses all IRB-approved materials and documents including the detailed protocol, IRB application, consent form, recruitment materials, questionnaires/data collection forms, and any other information relating to the research study.

A minor or administrative deviation is one that does not have the potential to negatively impact the rights, safety, or welfare of participants or others or the scientific validity of the study.

A major deviation is one that does have the potential to negatively impact the rights, safety, or welfare of participants or others or the scientific validity of the study.

APPENDIX 6: Reporting Timelines

Expedited Reporting Timelines				
Event	HRPO	QASMC	FDA	Pharmacyclics
Serious AND unexpected suspected adverse reaction			Report no later than 15 calendar days after it is determined that the information qualifies for reporting	Report no later than 15 calendar days after the event
Unexpected fatal or life-threatening suspected adverse reaction			Report no later than 7 calendar days after initial receipt of the information	Report no later than 15 calendar days after the event
Unanticipated problem involving risk to participants or others	Report within 10 working days. If the event results in the death of a participant enrolled at WU/BJH/SLCH, report within 1 working day.	Report via email after IRB acknowledgment		
Major deviation	Report within 10 working days. If the event results in the death of a participant enrolled at WU/BJH/SLCH, report within 1 working day.			
A series of minor deviations that are being reported as a continuing noncompliance	Report within 10 working days.			

Expedited Reporting Timelines

Event	HRPO	QASMC	FDA	Pharmacyclics
Protocol exception	Approval must be obtained prior to implementing the change			
Clinically important increase in the rate of a serious suspected adverse reaction of that list in the protocol or IB			Report no later than 15 calendar days after it is determined that the information qualifies for reporting	
Complaints	If the complaint reveals an unanticipated problem involving risks to participants or others OR noncompliance, report within 10 working days. If the event results in the death of a participant enrolled at WU/BJH/SLCH, report within 1 working day. Otherwise, report at the time of continuing review.			
Breach of confidentiality	Within 10 working days.			
Incarceration	If withdrawing the participant poses a safety issue, report within 10 working days.			

Expedited Reporting Timelines

Event	HRPO	QASMC	FDA	Pharmacyclices
	If withdrawing the participant does not represent a safety issue and the patient will be withdrawn, report at continuing review.			
Pregnancy/Other Malignancies/AESIs				Report no later than 15 days of learning of the event

Routine Reporting Timelines

Event	HRPO	QASMC	FDA
Adverse event or SAE that does not require expedited reporting	If they do not meet the definition of an unanticipated problem involving risks to participants or others, report summary information at the time of continuing review	Adverse events will be reported in the toxicity table in the DSM report which is typically due every 6 months.	The most current toxicity table from the DSM report is provided to the FDA with the IND's annual report.
Minor deviation	Report summary information at the time of continuing review.		
Complaints	If the complaint reveals an		

	unanticipated problem involving risks to participants or others OR noncompliance, report within 10 working days. If the event results in the death of a participant enrolled at WU/BJH/SLCH, report within 1 working day. Otherwise, report at the time of continuing review.		
Incarceration	
If withdrawing the participant poses a safety issue, report within 10 working days.
 
If withdrawing the participant does not represent a safety issue and the patient will be withdrawn, report at continuing review.

